Title	Response evaluation in myeloma patients using integrated ¹⁸ F- Fluorodeoxyglucose (¹⁸ F-FDG) positron emission tomography/magnetic resonance imaging (PET/MRI)			
Short title	REVAMP			
Start and End Dates of Study	Start Date: 01/10/16 End Date: 01/09/22			
Study design	Non-randomised single centre exploratory study			
Number of patients	20 patients with completed PET/MRI imaging at baseline and post therapy			
Primary objectives	1: To compare diagnostic accuracy of integrated ¹⁸ F-FDG PET/MRI with ¹⁸ F-FDG PET/CT at baseline and post-induction chemotherapy (prior to potential bone marrow transplantion).			
Secondary Objectives	 To develop, implement and assess software for lesional and global disease burden with integrated ¹⁸F-FDG PET/MRI (and PET & MRI separately) To assess the software repeatability for whole body and target lesional quantification To correlate ADC50-900 & fat fraction with i)clinical biomarkers including serum paraprotein level, bone marrow aspirate & ii)18-F FDG PET SUL; To correlate 18F FDG PET SUL with clinical biomarkers; To assess the lesional & inter-lesional heterogeneity of quantitative parameters (FF, ADC) using statistical radiomic methods. 			
Imaging	Research: Integrated 18F-FDG PET/MRI at baseline and following completion of induction chemotherapy. Comparator: - 1: Clinical assessment and clinical biomarkers 2: ¹⁸ F-FDG PET/CT and WB-MRI alone			
Endpoints	Response versus non-response to induction chemotherapy. Response versus non-response to transplantation. Time to relapse.			
Inclusion criteria	Referrals to our institution with suspected or newly diagnosed myeloma who are suitable to undergo ¹⁸ F-FDG PET/MRI and who are being considered for bone marrow transplantation.			
Exclusion criteria	 Contraindications to contrast-enhanced MRI or FDG-PET/CT. Other known primary malignancy. Patients not being considered for systemic disease control treatment. 			

3. Trial Schema

Potential participants identified, screened & approached Patient recruited & consented PET/CT & PET/MRI appointments booked: pre and post-treatment PET/CT & PET/MRI safety questionnaire completed Standard clinical pre-treatment assessments

Visit 1:

[figure not shown]
Baseline PET/CT & PET/MRI prior to potential treatment commencing

Visit 2:

Post-treatment PET/CT & PET/MRI within 4-6 weeks following completion of induction chemotherapy (only in patients diagnosed with myeloma).

Further management:

Treatment (which may include bone marrow transplant) and follow-up including whole body MRI as per clinical practice

Page 6 of 14

4. Background and Rationale:

Response assessment - a clinical challenge:

Multiple myeloma (MM) is a debilitating disease characterised by monoclonal plasma cell proliferation, affecting 4,800 patients/year [Cancer Research UK, 2014]. 80% of patients have lytic bone lesions at diagnosis. In recent years studies have shown that advanced imaging techniques e.g. whole body MRI (WBMRI) and CT have sensitivity and specificity of > 80% in detection of focal lesions [Regelink et al, 2013] whilst skeletal survey (SS) has a high false negative rate of 30-70% [Baur-Melnyk, AJR 2008, Fruehwald, Invest Radiol 1988]. This growing body of evidence supporting advanced imaging techniques has prompted a change in the International Myeloma Working Group (IMWG) guidelines for imaging evaluation of MM patients [Dimopoulos, 2015]. The IMWG now advocates use of WBMR in patients with solitary plasmacytoma and in asymptomatic/smouldering myeloma (SM).

WBMRI is a highly sensitive non-ionising radiation technique, and incorporation of diffusion-weighted and DIXON sequences provide additional quantitative information: apparent diffusion coefficient (ADC50-900, mm2/s) and fat fraction (%). WBMRI may improve lesion detection, staging accuracy, treatment response assessment, and influence clinical management when used complementary to conventional clinical/biochemical review. The emergence of WBMRI in clinical practice has highlighted a need for better quantitative tools to assess and quantify whole body disease burden and treatment response. At present 18F-FDG PET is reserved for problem solving in individual cases; it remains unclear how it compares to WBMRI, the latter having the advantage of no ionising radiation, although PET/CT may be superior in early treatment response assessment [Spinnato et al, 2012]. There has been limited work to date evaluating the potential additive value of integrated ¹⁸F-FDG PET in disease assessment in myeloma.

5. Hypotheses:

We hypothesise that: 1) combined PET/MRI will improve staging and response assessment of MM compared to PET/CT or WB-MRI alone, 2) lesion (SUV, ADC) or whole body quantitative imaging (including total tumour volume, ADC50-900, fat fraction) derived from an in-house multimodal software (FAST, KCL)) to assess MM tumour activity / burden can quantify disease at staging, & serial whole body metrics may improve treatment response assessment.

6. Aims:

6.1. Primary aims:

To compare diagnostic accuracy of PET/MRI tumour assessment with PET/CT and WB MRI alone in comparison with current reference standard (MDT review including clinical imaging and biomarkers, as assessed by consensus panel) in assessing staging and treatment response.

6.2. Secondary aims:

1: To develop, implement and assess software for lesional and global disease burden with integrated ¹⁸F-FDG PET/MRI (and PET & MRI separately)

2: To assess the software repeatability for whole body and target lesional quantification 3)To correlate ADC50-900 & fat fraction with i) clinical biomarkers including serum paraprotein level, bone marrow aspirate & ii)18-F FDG PET SUL;

4) To correlate changes in 18F FDG PET SUV and MRI ADC, FF with clinical biomarkers;

5) To assess the baseline and treatment-related changes in lesional & inter-lesional heterogeneity of quantitative parameters (FF, ADC) using statistical radiomic methods.

7. Study Plans

7.1. Study design:

Prospective non-randomised feasibility and pilot study in suspected or newly diagnosed transplant eligible MM patients planned for treatment. All patients will undergo integrated 18F-FDG PET/MRI immediately after 18F-FDG PET/CT (clinical routine) at baseline and, where a diagnosis of myeloma is confirmed on bone marrow biopsy, following completion of induction chemotherapy. Up to 20 completed datasets will be acquired. Patients not subsequently confirmed as having myeloma (based on clinical parameters including bone marrow biopsy) will be withdrawn from the study and will not undergo follow-up PET/CT and PET/MRI. Data for patients not subsequently confirmed as having myeloma will be used for research purposes (assessment of diagnostic accuracy as per primary study objective) unless consent is withdrawn.

7.2. Participants:

Adults (>18 years) with a suspected or new diagnosis of myeloma.

7.3. Inclusions:

Patients with suspected or new diagnosis of myeloma due to systemic disease control treatment.

7.4. Exclusions:

Pregnant females.

Concomitant uncontrolled medical conditions.

ECOG performance status > 2. Estimated prognosis < 12 weeks.

Contraindications to contrast-enhanced MRI or FDG PET/CT including significant renal impairment (eGFR < 50).

patients not being considered for systemic disease control treatment.

7.5. Imaging:

¹⁸F-FDG PET/CT (clinical routine) followed by research PET/MRI:

PET/CT: Following a 6hr fast, 400 MBq ¹⁸F-FDG will be administered. At 90 +/-5 mins p.i. imaging (GE Discovery PET/CT) will commence from vertex-feet as per clinical practice.

Following completion the patient will be imaged on Siemens mMR 3T PET/MRI from vertex-feet. Free-breathing DW-MRI (b50, 900s/mm²) sequences at the same bed positions will be obtained simultaneously to the PET acquisition. Corresponding T1 & T2 sequences will be acquired. A whole body contrast-enhanced MRI sequence will be obtained (*). Imaging will be repeated post-induction chemotherapy to assess response/non-response.

Quality assurance & control: Departmental processes & SOPs for scanner image acquisition QC will be followed. Additionally, phantom quantitation of ADC and SUV is performed as per normal departmental SOPs.

7.6. Follow up:

Patients will be reviewed in haematology outpatients as per institutional practice. Patients with suspected myeloma who are not confirmed to have myeloma subsequently with be withdrawn from the study. Routine clinical response assessment with other clinically appropriate tests for an individual patient as determined by the patient's haematologist as per institutional practice (including 100 day post bone marrow transplant bone marrow biopsy results where applicable). Follow-up imaging will include whole body MRI. Time to relapse will be assessed. The end of study definition is the patient's final clinic visit before discharge.

7.7. Image analysis:

Research PET/MRI imaging biomarkers

Target lesion(s): SUV_{max}, SUV_{mean}, SUL_{peak}, ADC_{mean and min}, rSI_{normalised}. These will be quantified using standard manufacturer software (Siemens/Hermes) following segmentation, thresholding, & volume-of-interest analysis.

Exploratory whole body parameters: WB-volumemri &/or PET, WB-SUVmean, WB-

ADC_{mean}, WB-rSI_{mean}, WB fat fraction.

Additional exploratory analysis will be performed using in-house developed software (FAST, KCL) to generate the above parameters. Inter-lesional heterogeneity will be assessed as the standard deviation (SD). The software will also enable intra-lesional heterogeneity to be quantified.

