8.0 Statistical Analysis

Feasibility and Pilot study

This is an exploratory study and therefore no formal sample size calculation has been performed.

Data:

Each patient will have PET/CT and PET/MRI at baseline. Patients with confirmed myeloma diagnosis will have a clinical PET/CT and research PET/MR following completion of induction chemotherapy.

Parameters estimated from this exporatory study:

Diagnostic accuracy: Sensitivity, specificity, PPV, NPV, accuracy will be assessed for 18F-FDG PET alone, CT alone, MRI alone 18-F FDG PET/CT, 18F-FDG PET/MRI compared to consensus MDM review.

Comparisons: Between tumour volume metrics will be assessed using appropriate parametric and non-parametric tests and via Mann-Whitney test, (if non-parametric data)

**Correlations:** Between quantitative MRI & 18F-FDG PET & correlations between quantitative imaging parameters & clinical biomarkers will be assessed using Spearman correlation (if non parametric).

Repeatability: Software repeatability will be assessed using Bland-Altman statistics Changes with treatment: Changes in tumour volume, ADC, fat fraction, SUV & heterogeneity will be assessed using Wilcoxon's signed rank test (if non-parametric data)

Procedure	Recruitment	Baseline	Post-treatment
Documentation			
PIS and consent signed	Х		
PET/CT & PET/MRI safety questionnaire passed		х	x
Inclusion & exclusion criteria met	х	х	х
Routine Investigations			
PET/CT		х	x
Research Investigations			
PET/MRI (no additional tracer injection)		х	Х

9. Summary of Procedures and Assessments

10. Data Collection:

Case Report Forms will be completed by the research team or designates.

11. Data monitoring:

Eligibility criteria will be reviewed by the data manager on potential recruitment of patients into the trial. Consent forms will be reviewed for accuracy, dates, signatures and completeness. The data stamp or version number of the patient information sheet and study protocol currently in use will form part of the normal eligibility criteria to ensure up to date study documentation are being used in the recruitment process. The data managers for completeness will check CRFs as data is entered into the database. Statistical data monitoring of the database will be performed at regular intervals to ensure completeness and accuracy of data.

12 Trial Monitoring:

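### The primary comparator differs between synopsis and section 6.1, and section 8 states no within-patient contrast of PET/MRI with PET/CT or WB-MRI, so the comparative objective is only partly answered

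*Protocol*

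**What the plan says.** The primary comparison appears in four places in the protocol.

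- Synopsis, primary objectives: "To compare diagnostic accuracy of integrated ¹⁸ F-FDG PET/MRI with ¹⁸ F-FDG PET/CT at baseline and post-induction chemotherapy". PET/CT is the only comparator.
- Synopsis, imaging row: both PET/CT and WB-MRI alone are listed as comparators, without saying whether both are primary.
- Section 5, hypothesis 1: "combined PET/MRI will improve staging and response assessment of MM compared to PET/CT or WB-MRI alone".
- Section 6.1: "To compare diagnostic accuracy of PET/MRI tumour assessment with PET/CT and WB MRI alone", judged against "MDT review including clinical imaging and biomarkers, as assessed by consensus panel", for staging and for treatment response.

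Section 8.0 then lists sensitivity, specificity, PPV, NPV and accuracy for "18F-FDG PET alone, CT alone, MRI alone 18-F FDG PET/CT, 18F-FDG PET/MRI compared to consensus MDM review". Its only item headed as comparisons concerns something else: "Between tumour volume metrics will be assessed using appropriate parametric and non-parametric tests and via Mann-Whitney test". The same section names Spearman correlation, Bland-Altman statistics and the Wilcoxon signed rank test for other analyses. It calls the study exploratory and says no formal sample size calculation was done.

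Under section 7.1, all patients have PET/MRI directly after PET/CT at baseline, and those with confirmed myeloma have both again after induction. Data from patients not confirmed as having myeloma are kept for the accuracy objective unless consent is withdrawn. The target is up to 20 completed datasets.

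**The concern.** The objective is to compare modalities, but the accuracy analysis compares each modality with the reference only. A reader of the results would have one set of accuracies per modality and would have to make the comparison by eye.

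Two things are at stake. First, the design is paired, and much of its information about the difference lies in the patients whom one modality classifies correctly and the other does not. Section 8 does not ask for those counts. Second, with five measures and five modalities, possibly at two visits, and no designated contrast, nothing in the protocol says which pair of figures answers the primary question. The disagreement over WB-MRI adds to this: under the synopsis objective it is not a primary comparator, under section 6.1 it is.

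**Working it through.** **Is there a figure to reproduce?** No. The protocol gives no alpha, power, effect size or expected accuracy. The check is a comparison of the texts, followed by an illustration with assumed counts.

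**Texts side by side.** PET/MRI versus PET/CT is common to all four statements. WB-MRI alone is in section 6.1, hypothesis 1 and the synopsis imaging row, and is missing from the synopsis objective. Both versions of the objective cover baseline and post-induction. Section 8 contains neither contrast: no difference, interval or test between modalities is given for any accuracy measure.

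**Do the separate accuracies determine the paired result?** Let *b* be the patients whom only PET/MRI classifies correctly, *c* those whom only PET/CT classifies correctly, and *n* the number of pairs.

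- Difference: d = (b − c)/n
- Approximate (Wald) standard error: √[(b + c) − (b − c)²/n] / n
- Exact two-sided McNemar: p = 2 × P(X ≥ b), where X is binomial with b + c trials and probability 0.5, and b > c

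The separate accuracies fix b − c but not b + c. Take n = 20 (the post-induction target) and assume PET/MRI correct in 18 and PET/CT in 12. Then b − c = 6, and c can be 0, 1 or 2 because PET/MRI is wrong in only two patients.

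| b / c | d | Exact p | Approximate 95% CI |
|---|---|---|---|
| 6 / 0 | 0.30 | 2 × 1/64 = 0.031 | 0.10 to 0.50 |
| 7 / 1 | 0.30 | 2 × 9/256 = 0.070 | 0.06 to 0.54 |
| 8 / 2 | 0.30 | 2 × 56/1024 = 0.109 | 0.02 to 0.58 |

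For the first row, the standard error is √(6 − 36/20)/20 = 0.102, and 1.96 × 0.102 = 0.20. The half-widths in the other rows are 0.24 and 0.28. The separate exact (Clopper-Pearson) intervals, 0.683 to 0.988 and 0.361 to 0.809, are identical in all three rows.

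With a smaller assumed gap, 18/20 versus 16/20 (d = 0.10), the possible discordant counts are 2/0, 3/1 and 4/2. The p-values are 0.50, 0.625 and 0.69, and the lower limits −0.03, −0.09 and −0.14.

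In the second and third rows of the table the Wald interval excludes zero while the exact p exceeds 0.05. The Wald form is too rough to be the reported interval at this size and is used here only to show how precision varies.

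**What can 20 pairs show?** Under assumed discordance rates (PET/MRI only correct / PET/CT only correct) and an assumed two-sided 0.05 level, exact McNemar power is:

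- 20% / 5%: 9.5%
- 25% / 5%: 20%
- 30% / 5%: 32%
- 40% / 5%: 58%

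The expected half-width at 20% / 5% is 1.96 × √[(0.25 − 0.15²)/20] = 0.21, and at 40% / 5% it is 1.96 × √[(0.45 − 0.35²)/20] = 0.25. These figures concern overall correct or incorrect calls. Sensitivity and specificity each use only part of the patients, so their intervals would generally be wider.

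**The case against.** The best case for the plan is that section 8 already gives the measures, the modalities and the reference, and that the method for a paired difference is commonly left to an analysis plan, which is not at hand. Section 8 does not prescribe an unpaired analysis of accuracy; it is silent. Section 6.1 itself frames the comparison through the common reference, so scoring each modality against it is the required first step. And only one line, the synopsis objective, omits WB-MRI.

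Much of this stands. A reader might infer that section 8 does not address the primary objective at all; that goes too far, because the separate accuracies permit a descriptive side-by-side reading. The choice of interval formula may also wait for an analysis plan. What does not fall away is that the protocol names methods for its secondary analyses and no contrast at all for its primary one, and that its two statements of the primary comparator would still differ whatever an analysis plan says.

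Three further inferences are not supported:

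- **That at most 20 pairs are available throughout.** This holds post-induction. At baseline, patients not confirmed as having myeloma also have both scans and count towards accuracy, so there may be more than 20 pairs.
- **That the trial is underpowered for a superiority claim.** No test of accuracy or power is stated, and the study calls itself exploratory.
- **That hypothesis 1 must be reworded.** It is introduced as a hypothesis, and section 8 speaks of parameters to be estimated.

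**Conclusion.** The point holds as a moderate one that should be corrected. The protocol disagrees with itself on whether WB-MRI alone is a primary comparator, and section 8 answers the comparative objective only in part. In the illustration, the same pair of accuracies is compatible with p from 0.031 to 0.109 and approximate half-widths from 20 to 28 points, so the planned output leaves the precision of the main comparison undetermined.

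The conclusion about the text rests on no assumption. The numbers rest on assumed counts, n = 20 and one overall call per patient and modality. The power range of about 10% to 58% shows only why an estimate with an interval is a more realistic aim than a test; it is not a property that the trial promised and misses. Nor do the documents give a reason to make one visit the sole primary time point, since both versions of the objective keep baseline and post-induction.

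**What to change.** 1. **Synopsis and section 6.1:** use one wording for the primary comparison and state whether WB-MRI alone is a primary or a secondary comparator. The sponsor must choose; PET/MRI versus PET/CT is the contrast common to every version.
2. **Section 8:** state the primary analysis as the within-patient difference, PET/MRI minus PET/CT, in sensitivity and in specificity against the same MDM reference. Report it separately for baseline (all patients scanned, including those not confirmed as having myeloma) and for post-induction (up to 20 patients). Give a paired confidence interval suited to small samples and the discordant counts, with exact McNemar as support only.
3. **WB-MRI and component modalities:** if WB-MRI alone is kept as a primary comparator, give it the same paired contrast. Present PET alone, CT alone and, if it is not primary, MRI alone as secondary.

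The cost is wording in the synopsis and sections 6.1 and 8. No extra scans or patients are needed, and the per-patient calls are already required to compute the accuracies. The drawback is that the wide intervals will be visible, particularly for specificity if few patients are negative on the reference.

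### As Section 6.1 is worded, the routine PET/CT very likely enters the reference standard that judges it, while the research PET/MRI is not named there

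*Protocol*

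**What the plan says.** Section 6.1 of the protocol sets the primary aim: the accuracy of PET/MRI is compared with that of PET/CT and of whole body MRI (WB-MRI) alone, for staging and for treatment response. The yardstick is the "current reference standard (MDT review including clinical imaging and biomarkers, as assessed by consensus panel".

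Section 8.0 carries this into the analysis. Sensitivity, specificity, predictive values and accuracy are to be estimated for PET, CT and MRI singly and for "18-F FDG PET/CT, 18F-FDG PET/MRI compared to consensus MDM review".

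The two main tests have different standing throughout:

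- Section 7.1: "All patients will undergo integrated 18F-FDG PET/MRI immediately after 18F-FDG PET/CT (clinical routine) at baseline".
- Section 7.5: "FDG PET/CT (clinical routine) followed by research PET/MRI".
- Section 8.0, Data: "Patients with confirmed myeloma diagnosis will have a clinical PET/CT and research PET/MR following completion of induction chemotherapy".
- Section 9: PET/CT is listed among the routine investigations and PET/MRI among the research ones, each at baseline and post-treatment.

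Two further statements bear on the point. Under Section 7.1, data from patients in whom myeloma is not confirmed "will be used for research purposes (assessment of diagnostic accuracy as per primary study objective) unless consent is withdrawn". Under Section 7.6, "Follow-up imaging will include whole body MRI".

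**The concern.** A test that helps to form its own reference standard is favoured by that standard. If the consensus panel reads the PET/CT as part of the clinical imaging, PET/CT is judged partly against itself. A PET/MRI that the panel does not see has no such help. The patients who decide the comparison are those in whom the two tests disagree, and in them a panel informed by PET/CT tends to side with it. A lesion seen only on PET/MRI may then count as a false positive.

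The likely effect is to overstate the accuracy of PET/CT and understate that of PET/MRI. That works against the first hypothesis in Section 5, that PET/MRI improves staging and response assessment, and could hide a real gain. It is bias rather than imprecision, so enrolling more patients would not remove it.

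The exposure is uneven. Whether a patient has myeloma is confirmed with bone marrow biopsy (Section 7.1), which limits the damage there. Staging and treatment response, the two targets of Section 6.1, are less protected.

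**Working it through.** The protocol states no figure on this point, so there is none to reproduce. The check has a textual part and an illustration.

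**Does PET/CT enter the reference?**

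1. Section 6.1 admits clinical imaging to the reference and does not list which scans.
2. At the two time points of the primary objective, baseline and post-induction, PET/CT is the only scan the protocol labels as clinical or routine (Sections 7.1, 7.5, 8.0 and 9). Clinical WB-MRI is named only for follow-up (Sections 3 and 7.6).
3. No sentence withholds PET/CT from the panel or masks the panel to it.
4. PET/MRI is labelled research throughout. No sentence places it in the reference, and none excludes it.

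Steps 1 to 3 make PET/CT a very likely part of the reference. This is a strong inference, not stated text.

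**How large could the effect be?**

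Assume a per-patient, two-category call. Let n be the patients analysed, k the number in whom PET/CT and PET/MRI disagree, and f the fraction of those k in whom the panel sides with PET/CT. In each disagreement exactly one test matches the panel, and patients in whom the tests agree add equally to both. So:

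apparent accuracy difference (PET/CT minus PET/MRI) = [kf - k(1 - f)]/n = k(2f - 1)/n

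If the tests are truly equally accurate, an unbiased panel has f = 0.50 and the difference is 0. The 20 completed datasets come from the synopsis and Section 7.1. The 20% discordance (k = 4 at n = 20) and the values of f are assumptions.

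| f | Calculation | Apparent difference |
|---|---|---|
| 0.25 | 4 x (-0.5)/20 | -10 points |
| 0.50 | 4 x 0/20 | 0 points |
| 0.75 | 4 x 0.5/20 | +10 points |
| 1.00 | 4 x 1/20 | +20 points |

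At a fixed discordance rate these do not depend on n: k = 6 at n = 30 gives the same values. They scale with discordance. Both scans use one tracer injection (Section 9), so PET errors may be shared and discordance lower. At 10% (k = 2 of 20, assumed) the four values halve to -5, 0, +5 and +10.

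**Leverage of one patient.** If the panel follows a wrong PET/CT over a right PET/MRI, PET/CT gains 1/n and PET/MRI loses 1/n, a shift of 2/n. After induction, with n at most 20, that is at least 2/20 = 10 points. At baseline n may exceed 20, because unconfirmed patients stay in the accuracy assessment: 2/25 = 8 points, 2/30 = 6.7 points (n = 25 and 30 assumed).

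**Cross-check with a second model.** Suppose the reference equals the PET/CT result with probability g and the truth otherwise, with independent errors and true accuracies a(CT) and a(MR). Apparent accuracy is g + (1 - g)a(CT) for PET/CT, and g[a(CT)a(MR) + (1 - a(CT))(1 - a(MR))] + (1 - g)a(MR) for PET/MRI. All inputs are assumed.

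- Both truly 80%: at g = 0.10, 0.25 and 0.50, PET/CT against PET/MRI is 82% v 78.8%, 85% v 77% and 90% v 74%. The spurious PET/CT advantage is 3.2, 8 and 16 points.
- PET/CT 80%, PET/MRI 90%: the true 10-point gain for PET/MRI becomes +6.4, +1.0 and -8.0 points.

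This model lets only PET/CT pull the panel, and independent errors imply discordance of 1 - 0.68 = 32% in the equal-accuracy case. It therefore shows the mechanism in one direction and at high discordance. The first table is the fairer range.

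**The case against.** The strongest reply is that Section 6.1 never names PET/CT. Section 4 describes FDG PET as currently kept for particular problem cases and WB-MRI as entering clinical practice, so the clinical imaging could be largely MRI. This does not displace Section 7.1, under which every patient has PET/CT as clinical routine. It does mean that PET/CT in the reference is an inference.

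Second, a reader might infer that the panel holds PET/CT and is denied PET/MRI. The documents do not say so. The Section 6.1 wording is not an exhaustive list, and Section 15.5, on co-reporting by two radiologists, does not keep PET/MRI from the panel. If the panel saw both, the imbalance would shrink, but both tests would then be inside their own reference and the results would be agreement rather than accuracy.

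Third, a reader might see a contradiction with the synopsis, which lists "Comparator: - 1: Clinical assessment and clinical biomarkers" separately from PET/CT and WB-MRI. That is a list of comparators. It neither defines a reference standard nor says what the panel sees, so it supports no contradiction.

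Fourth, follow-up WB-MRI may pull the panel towards MRI findings, so the direction is not fixed. This stands, and is why the range includes f below 0.50. At the other end, f = 1.00 is an extreme for a panel that also weighs biomarkers.

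Finally, the study is an exploratory pilot with no formal sample size, and a composite reference is a recognised compromise when not every lesion can be biopsied. That lowers the consequence but does not remove the point: accuracy is the primary aim, and the protocol itself fixes the reference. A later plan that excluded the PET/CT would have to depart from Section 6.1 on its plain reading.

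**Conclusion.** The concern holds as a strong inference from the text. PET/CT very likely forms part of the reference that judges it, and PET/MRI is not named as part of that reference. The result is incorporation bias in the primary comparison, most likely favouring PET/CT for staging and response, with patient-level myeloma status partly protected by biopsy.

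The stronger claim, that PET/CT certainly is in the reference and certainly benefits, goes beyond the documents. The size is not derivable from the protocol. The range of -10 to +20 points rests on a per-patient binary call, equal true accuracy, 20% discordance and f between 25% and 100%. Lower discordance narrows it in proportion. The sponsor should correct this, at moderate priority given the exploratory purpose.

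**What to change.** In Sections 6.1 and 8.0:

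- **Patient-level diagnosis and treatment response.** State that the consensus panel sets the reference from bone marrow, paraprotein and other biomarkers, and clinical course, without the PET/CT, PET/MRI or WB-MRI reads under test.
- **Lesion-level staging.** Imaging is unavoidable here, so give the panel PET/CT and PET/MRI on equal terms and report the results as agreement, not accuracy.
- **Follow-up WB-MRI.** Do not treat it as a neutral reference. MRI is itself an index test and half of PET/MRI, so it could replace a tilt towards PET/CT with one towards PET/MRI. Nor is it assured for unconfirmed patients, who are withdrawn (Sections 7.1 and 7.6) although their data stay in the accuracy assessment.

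The cost is a change of wording and one instruction to the panel, with no extra scans or patients. The price in interpretation is that lesion-level results support only statements of agreement, and the patient-level reference carries no imaging information.

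### The bone marrow aspirate is to be correlated with ADC and fat fraction, but no listed imaging value is measured at the aspirated marrow site, so a weak correlation could not be interpreted

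*Protocol*

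**What the plan says.** **The aim.** Section 6.2 of the Protocol plans "3)To correlate ADC50-900 & fat fraction with i) clinical biomarkers including serum paraprotein level, bone marrow aspirate". The synopsis carries the same objective.

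**The measurements.** Section 7.7 lists imaging values at two levels.
- Lesion level: "Target lesion(s): SUV_{max}, SUV_{mean}, SUL_{peak}, ADC_{mean and min}, rSI_{normalised". According to the same section, "These will be quantified using standard manufacturer software (Siemens/Hermes) following segmentation, thresholding, & volume-of-interest analysis".
- Whole-body level: "Exploratory whole body parameters: WB-volumemri &/or PET, WB-SUVmean, WB", continued as "ADC_{mean}, WB-rSI_{mean}, WB fat fraction".

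The in-house software adds no further region: "Additional exploratory analysis will be performed using in-house developed software (FAST, KCL) to generate the above parameters". It also gives heterogeneity within and between lesions.

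**The analysis.** Section 8.0 says that "correlations between quantitative imaging parameters & clinical biomarkers will be assessed using Spearman correlation (if non parametric". It does not say which imaging value is paired with which biomarker.

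The Protocol names neither the aspirate site nor a reference region in sampled or background marrow.

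**The concern.** An aspirate describes the marrow at one skeletal site. A target lesion is chosen because it is focal, and it may lie elsewhere. A whole-body mean covers the sampled site, if at all, as a small part of a large average. Neither is matched to the tissue that supplied the biomarker.

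What is at stake is how the result can be read. If the observed correlation is low, one reading is that ADC and fat fraction do not follow marrow infiltration. Another is that the imaging value came from other tissue or was diluted. The planned data do not distinguish between the two. In a pilot of 20 completed datasets, whose results may decide which imaging markers are carried forward, a useful marker could be dropped for the wrong reason.

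**Working it through.** **Step 1: match the aim to the measurement list.**

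| Value needed for the aspirate correlation | Target lesion (7.7) | Whole body (7.7) | Aspirated site |
|---|---|---|---|
| ADC | mean and minimum | mean | not listed |
| Fat fraction | not listed | listed | not listed |

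For fat fraction, the whole-body value is the only listed candidate. Aim 5 in section 6.2 speaks of lesional heterogeneity of fat fraction and so presupposes a lesion value, but 7.7 does not list one. A patient without a focal target has no lesion ADC and is left with the whole-body values.

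**Step 2: is there a planned figure to reproduce?** No. Section 8.0 states that no formal sample size calculation was made, and gives no target correlation, significance level or power. What follows is an illustration.

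**Step 3: illustrate the effect of attenuation.**

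Inputs:
- n = 20 completed datasets (synopsis and section 7.1).
- Correlation of a site-matched imaging value with the aspirate: 0.6 (assumed; range 0.5 to 0.7).
- Correlation of the value actually used with the site-matched value: 0.7 (assumed; range 0.5 to 0.8).
- Two-sided significance level 5% (assumed).

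Expected correlation after mismatch = 0.6 × 0.7 = 0.42. The product rule assumes that the value used is related to the aspirate only through the site-matched value.

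For a Spearman correlation on the Fisher scale with variance 1.06/(n − 3):

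power ≈ Φ( atanh(ρ) × √((n − 3)/1.06) − 1.96 ), and √(17/1.06) = 4.005.

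- ρ = 0.6: 0.693 × 4.005 − 1.96 = 0.82, power about 79%. The approximate 95% interval around an observed 0.6 is 0.20 to 0.83.
- ρ = 0.42: 0.448 × 4.005 − 1.96 = −0.17, power about 43%. The approximate 95% interval around an observed 0.42 is −0.04 to 0.73.

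A simulation of the Spearman test (20,000 runs) gave 77% and 42%, so about 78% and about 43% are fair summaries.

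**Step 4: range over the assumptions, n = 20.**

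| Site-matched ρ | Power, matched | Power, factor 0.8 | Power, factor 0.7 | Power, factor 0.5 |
|---|---|---|---|---|
| 0.5 | 59% | 40% | 31% | 17% |
| 0.6 | 79% | 55% | 43% | 24% |
| 0.7 | 93% | 72% | 57% | 31% |

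The direction is the same throughout. The size depends wholly on the assumed inputs.

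**The case against.** **The aim can be read as global.** The Protocol groups the aspirate with serum paraprotein as a clinical biomarker, and its second hypothesis concerns lesional or whole-body burden. It nowhere claims to validate ADC or fat fraction against local histology. On that reading, correlating whole-body imaging with the aspirate is coherent. This stands as a reason to keep the whole-body correlation, but it does not make a weak result interpretable.

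**The choice of VOI could be left to a SAP or imaging manual.** This stands in part. The scans run from vertex to feet, so the region could be drawn later. But 7.7 is the Protocol's own measurement list, and a SAP cannot analyse a VOI that nobody drew, or place it correctly if the aspirate site and side were not recorded.

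**Stronger readings that the documents do not support.**
- A reader might infer that patients without focal disease drop out of the aim. They do not: whole-body ADC and fat fraction are listed regardless of focal disease.
- A reader might take "80% of patients have lytic bone lesions at diagnosis" from section 4 and compute 20 × (1 − 0.80) = 4 patients without a target, leaving 16 (power about 35% at ρ = 0.42). The 80% concerns lytic lesions. The Protocol does not define a target lesion as lytic, and targets are read on PET/MRI. The smaller number would also apply only to lesion ADC, and not to the whole-body values.
- A reader might infer that imaging and aspirate always describe different tissue. A whole-body value may include the sampled site in diluted form, and in diffuse disease the attenuation is less certain.

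**The study is exploratory.** Power at 5% is not a planned criterion here. The wider point survives, because attenuation biases the estimate itself and not only a test.

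**Conclusion.** The concern holds as a gap between one secondary aim and the Protocol's measurement list. None of the listed ADC or fat fraction values is measured at the aspirated marrow, so a weak correlation could reflect mismatch or dilution as well as lack of association. For fat fraction the gap is wider than for ADC, because only a whole-body value is listed.

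Attenuation is the plausible direction, but the Protocol gives no basis for its size. The fall in power from about 78% to about 43% at n = 20 rests on the assumed 0.6 and 0.7 and on the product rule, and should be cited only as an illustration. The point affects the interpretation of one component of aim 3 and leaves the primary objective untouched. It is a cheap improvement worth making.

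**What to change.** - **Section 7.7:** add one predefined marrow VOI at the skeletal site of the aspirate, on the opposite side if the scan follows the biopsy. Measure mean ADC, fat fraction and SUL there at baseline. Do so at the post-induction visit only where a routine aspirate of about the same date exists: the procedures table in section 9 lists no marrow sampling, and section 7.6 names only the biopsy 100 days after transplant, where applicable.
- **Case report form:** record the site and side of each aspirate.
- **Sections 6.2(3) and 8.0:** name this VOI as the main imaging variable for the aspirate correlation. Keep the whole-body and lesion values as additional correlates of the aspirate, and for paraprotein and disease burden.

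**Cost:** one extra VOI per scan, on images already acquired, and one extra recorded field. No additional scan or patient procedure is needed.
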